#### 6.10.2 Imputation Rules for Incomplete Dates

As a general principle, no imputation of missing data for variables will be done. Exceptions are the start and stop dates of AEs and concomitant medication. The imputed dates will be used to allocate the concomitant medication and AEs to a treatment group, in addition to

determining whether an AE is/is not treatment emergent. Listings of the AEs and concomitant medications will present the actual partial dates; imputed dates will not be shown.

#### 6.10.2.1 Imputation Rules for Diary Dates

Not Applicable.

#### 6.10.2.2 Imputation Rules for Adverse Events

For AEs, a missing or incomplete onset date will be imputed according to the following conventions.

If an onset date is missing or only the year is known, the imputed onset date will be the date of first dose of study drug.

If only the year is known for the AE onset date, the imputed onset date will be the latest of the following non-missing dates:

- Date of first dose of study drug
- January 1 of the year of AE onset date

If only the month and year is known for the onset date, set the surrogate onset date to the first day of that month and then apply the following rules.

- If the month and year of the onset date is prior to the month and year of the first dose of study drug, then the surrogate onset date will be the imputed onset date.
- If the month and year of the onset date is on or after the month and year of the first dose of study drug, then the imputed onset date will be the latest of the following non-missing dates:
  - Date of first dose of study drug
  - Surrogate onset date

If the imputed onset date is after the adverse event end date, the imputed onset date will be the same as the adverse event end date.

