### 5.4.1 Adverse Events

AEs will be coded using MedDRA. A TEAE is defined as an AE observed after starting administration of the IP until 30 days after the final administration of IP. If the adverse event occurs on Day 1 and the onset check box on the (AE) eCRF is marked "Onset after first dose of study drug" or the onset check box is left blank, then the adverse event will be considered treatment emergent. If the adverse event occurs on Day 1 and the onset check box is marked "Onset before first dose of study drug", then the adverse event will not be considered treatment emergent. If a subject experiences an event both during the pre-investigational period and during the investigational period, the event will be considered as TEAE only if it has worsened in severity (i.e., it is reported with a new start date).

A drug-related TEAE is defined as any TEAE with at least possible relationship to study treatment as assessed by the investigator or with missing assessment of the causal relationship.

AEs may be upgraded by the sponsor according to the Important Medical Event process.

A drug-related TEAE is defined as any TEAE with at least a possible relationship to study treatment as assessed by the investigator or with a missing assessment of the causal relationship.

Common TEAEs are defined as preferred terms (PTs) that have been reported by at least 5% of the subjects, in any treatment group.

When an AE start or stop date is missing, the date will be imputed using the rules in Section 6.10.2.2.

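### SAP 6.10.2.2 has two defects for AE onsets known only by year: two rules that conflict for a later year, and no branch that keeps an earlier year pre-dose

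*SAP*

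**What the plan says.** SAP 6.10.2.2 has two consecutive sentences that both cover an onset known only by year.

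- First sentence: "If an onset date is missing or only the year is known, the imputed onset date will be the date of first dose".
- Second sentence: "If only the year is known for the AE onset date, the imputed onset date will be the latest of the following non-missing dates". The two candidates are the first-dose date and "January 1 of the year of AE onset date".

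Neither sentence is given priority. For an onset known by month and year, the same section does have a branch for a month before the first-dose month: "then the surrogate onset date will be the imputed onset date", which leaves the event pre-dose. A closing rule covers all cases: "If the imputed onset date is after the adverse event end date", the onset moves back to that end date.

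SAP 6.10.2 states what the dates are for: "The imputed dates will be used to allocate the concomitant medication and AEs to a treatment group", and also to decide whether an event is treatment emergent. SAP 5.4.1 gives the definition: "A TEAE is defined as an AE observed after starting administration of the IP until 30 days after the final administration of IP". For events on Day 1 it adds a check box. If the box is marked as before first dose, the event is not a TEAE; if "the onset check box is left blank, then the adverse event will be considered treatment emergent". SAP 6.5 splits the safety tables into 25 mg and 50 mg columns, with separate sub-columns for subjects who escalate.

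**The concern.** A programmer has two instructions for one kind of record and must choose between them. The choice can move an event between dose columns in the safety tables, and safety is a secondary objective in both documents. Separately, neither instruction respects a recorded year that rules out onset on treatment, although the month-and-year rule beside them does. Counting an event of unknown onset as treatment emergent is a normal conservative convention. Doing so when the recorded year shows that onset came before dosing is an error. SAP 6.10.2 keeps imputed dates out of the listings, so a reader could see the partial date but not which rule was applied.

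**Working it through.** The plan gives no figure to reproduce here, so the check applies the rules as written. Rule 1 gives first dose. Rule 2 gives max(first dose, 1 January of onset year).

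**Inputs.** Dosing lasts 84 days, so last dose is first dose + 83 days (12-week treatment, both documents). The TEAE period ends 30 days after last dose (SAP 5.4.1), at first dose + 113 days. Escalation is taken at 28 or 56 days after first dose (weeks 4 and 8). Screening is taken as 7 to 17 days: week -1 in the protocol's Schedule of Assessments, Day -17 in SAP Table 5. There are 249 subjects, 166 planned for 50 mg (SAP 3), which leaves 249 - 166 = 83 on 25 mg. Even accrual over the calendar year is assumed; the documents do not give the accrual pattern.

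**Onset in the first-dose year.** 1 January of that year is never after first dose, so both rules give first dose and there is no conflict.

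**Onset in the year after first dose.** The imputed dates always differ.

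- Example: first dose 9 November 2020, escalation 7 December 2020, onset recorded as 2021. Rule 1 gives 9 November 2020 (25 mg column). Rule 2 gives 1 January 2021 (50 mg up-titrated column).
- Same subject escalated at week 8, on 4 January 2021: both dates precede escalation, so both rules give the 25 mg column.
- TEAE status: for the TEAE period to reach the next year, first dose + 113 days must be 1 January or later, so first dose lies from 10 September to 31 December. That is 21 + 31 + 30 + 31 = 113 dates. For each, both imputed dates lie inside the TEAE period, so status differs for 0 of 113.
- Dose column: it differs only if escalation is on or before 1 January. At 28 days, first dose must be no later than 4 December: 21 + 31 + 30 + 4 = 86 dates. At 56 days, no later than 6 November: 21 + 31 + 6 = 58 dates.
- Share of escalating 25 mg subjects: 86/365 = 24% and 58/365 = 16%. If all 83 escalated, that is 83 × 86/365 ≈ 20 or 83 × 58/365 ≈ 13 subjects. The number who escalate is not given, so these are ceilings under even accrual.

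**Onset in the year before first dose.** 1 January of an earlier year always precedes first dose, so both rules give first dose. Take first dose 6 January 2021:

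| Recorded onset | Recorded end | Imputed onset | TEAE by date |
|---|---|---|---|
| 2020 | ongoing, or 20 January 2021 | 6 January 2021 | yes |
| 2020 | 2 January 2021 | 2 January 2021 (end-date rule) | no |
| December 2020 | ongoing | 1 December 2020 | no |

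The first and third rows both establish a pre-dose onset, yet are classified differently. Protocol 7.3.1 collects AEs from consent, so the relevant interval is screening: 7/365.25 = 1.9% to 17/365.25 = 4.7% of subjects cross a year-end, or about 5 to 12 of 249. At 14 days it is 3.8%, about 10.

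**The case against.** The strongest defence is that the SAP limits the damage itself.

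- The end-date rule removes any prior-year event that ended before first dose. This stands.
- The Day 1 check box removes an event marked as starting before first dose. This stands only if the box is applied to dates imputed to Day 1, which the SAP does not say; a blank box makes the event a TEAE.
- SAP 5.4.1 also says that an event present both before and during the investigational period is a TEAE only if it worsened. That might catch some ongoing events, but the SAP does not say how it works with an imputed onset.

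It is also fair that year-only onsets should be rare with visits about four weeks apart, and that the listings show the actual partial dates.

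A reader might infer three stronger things, and the documents support none of them. One is that the conflict between the sentences changes TEAE status; it does not for any event inside the TEAE period. Another is that every prior-year event becomes a TEAE; the end-date rule alone refutes that. The third is that about 31% of subjects are exposed, since treatment plus 30 days is 114 days and 114/365 = 31%. That figure describes neither harm: the TEAE error depends on the screening period, and the column change needs a 25 mg subject who escalated by 1 January.

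**Conclusion.** Both defects are in the current SAP text, and both are small. The rule conflict can change the dose column, but not TEAE status, for 25 mg subjects who escalated by 1 January: about 16% (week 8 escalation) to 24% (week 4) of escalating subjects have dates that allow it. The missing prior-year branch can turn a known pre-dose event into a TEAE in the starting-dose column of either arm; about 2% to 5% of subjects have a screening period that allows it. These shares assume even accrual and full dosing, and would be higher if first doses clustered before (conflict) or just after (missing branch) a year-end, and near zero if they fell well away from one. They count subjects whose dates permit the problem, not events: an event with a year-only onset is also needed. The documents do not give the number of such events, and few are expected. The efficacy analysis and sample size are unaffected.

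**What to change.** In SAP 6.10.2.2:

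1. Remove the year-only alternative from the first sentence, so that it covers only a wholly missing onset.
2. Make the year-only rule: if the onset year is before the year of first dose, the imputed onset is 1 January of the onset year, and the event is pre-dose; otherwise it is the later of first dose and 1 January of the onset year.

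This mirrors the surrogate date in the month-and-year rule and always yields a date. It would also help to state in SAP 5.4.1 whether the Day 1 check box applies to imputed Day 1 dates.

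The cost is two sentences, or three with the check-box clarification, plus the matching change in the derivation program. No new data are needed. SAP Appendix 9.1 reports all 249 subjects as randomized, so AEs with a year-only onset can be counted directly to confirm how many are affected.

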#### 6.10.2.3 Imputation Rules for Concomitant Medications

In case of missing partial start and stop dates for concomitant medications, the following rules will be used:

If the start date is missing or partial:

- if the month is missing, use January
- if the day is missing, use the first day of the month under consideration
- if the year is missing, use year of the informed consent date
- if the entire date is missing, use informed consent date

If the stop date is missing or partial:

- if the month is missing, use December
- if the day is missing, use the last day of the month under consideration

• if the year or the entire date is missing, set the stop date to December 31st, 2099

If the imputed start date is after the stop date, then the imputed start date will be 1 day prior to the stop date.

#### 6.10.3 Outliers

All values will be included in the planned analyses. A sensitivity analysis excluding outliers may be performed as an additional secondary analysis, if considered appropriate by the study statistician or the medical expert.

## 7 **REVISION AND RATIONALE**

### 7.1 List of Changes in SAP Version 2.0 from Version 1.0

The changes from the approved SAP Version 1.0 (Dated 09-Dec-2020) to Version 2.0 that impact analyses are listed with the rationale in the table below.

SAP Sections	Description	Rationale
5	Table for classifying assessments as daytime or nighttime is added	Added for clarification
	Text for procedure for calculating efficacy endpoints	Added for clarification
5.1	Second paragraph: "total number of" should be "mean number of"	Corrected the definition of mean number of micturitions
5.2	Summary of efficacy data will also be done for EoT values	Added to be consistent with other studies.
	The success rate of efficacy variables in each treatment group initiated with either 50 mg or 25 mg dose will NOT be evaluated at each treatment visit	Not applicable
5.2.4	Section 5.2.4 was added to explain how the number of urge incontinence episodes are calculated	Was missing in Version 1
5.2.5	Text added how to deal if not all questions for OABSS are answered. Definition of baseline assessment was added.	Added for clarification
5.4.1	Corrected definition of TEAE	To be consistent with protocol
	Common TEAEs are defined as preferred terms (PTs) that have been reported by at least 5% of the subjects, in any treatment group.	Added "in any treatment group" to be consistent with other studies.
	Table 3 was updated	Based on new information
5.5.2	Text on compliance is updated	For clarification
6.4.1.3	Text on the "statistical comparison within each group" was added	To be consitent with analysis of micturition data.
6.5.1	Text regardind "upgraded according to the Important Medical Event process" was added.	Text added to be consistent with other studies
6.4, 6.5.2 – 6.5.4, and 6.5.6.1	Summary of efficacy, Lab, ECG, Vital signs and PVR data will also be done for EoT values	Added for clarification.

SAP Sections	Description	Rationale
6.5.2	Text adjusted for local laboratories and how to deal with Blood Urea and BUN results	To clarify how these data will be processed
	Text added on normalizing local lab data	To clarify how this will be done
6.5.4	Definition of QTcF was added	Added for clarification
6.10.1	Table 5 is updated	For bladder and questionnaire data no gaps in the windows are allowed, see new SAP template
9.1	The algorithm for pooling sites is added	This should be defined before Database Lock.

## 7.2 List of Changes in SAP Version 3.0 from Version 2.0

The changes from the approved SAP Version 2.0 (Dated 06-May-2021) to Version 3.0 that impact analyses are listed with the rationale in the table below.

SAP Sections	Description	Rationale
6.2.3	Results of Prior OAB Treatment will be summarized	Added for clarification
	Medical History data will be summarized	Addional request
6.4.1.2	Text added that 2 additional figures will be presented	Added for clarification
6.4.2.4	Section added to describe that for two secondary endpoints a figure will be presented	Additional request

## 9 APPENDICES

### 9.1 **Pooling of Sites Algorithm**

Two hundred and forty-nine (249) subjects were randomized at 15 sites. When "site" is included as a factor in a statistical model, sites that have less than 8 FAS subjects in total will be identified and then combined for statistical analysis purposes according to the following algorithm:

- Step 1: Divide the sites into two groups with Group 1 including all sites that have at least 8 FAS subjects and Group 2 including all remaining sites. Sort each group in ascending order by total sample size and site number.
- Step 2: Starting at the top of the Group 2 list (i.e., the first site with the smallest total sample size), combine the minimum number of sites required to achieve a "pooled site" that has at least 8 FAS subjects in total. Continue forming "pooled sites" in this manner until all Group 2 sites have been grouped or it is no longer possible to form a "pooled site" with at least 8 FAS subjects in total.
- Step 3: If there is a site (or several sites) left after step 2, combine the site(s) with the last "pooled site" that is created. For the situation where no previous "pooled site" is created, combine the site(s) with the first site on the sorted Group 1 list.
- "Pooled site" will be assigned names PoolSite01, PoolSite02, etc. For sites not
  needing to be pooled, the original site name will be used such as Site001. For all sites
  that have been combined into pooled sites, the assigned pooled site will be used
  instead of the original site identification in all statistical models that include "site" as
  a factor. However, the original site identification will be used in all summaries of
  subject disposition or discontinuation by site and in all data listings.

## 9.2 List of Excluded Concomitant Medications

Any medication used for the management of OAB (including tricyclic antidepressants, 1st generation H1-antagonists and alpha-blockers) and any drugs that are sensitive CYP2D6 substrates with a narrow therapeutic index and sensitive P-gp substrates.

Use of these medications is not permitted during the study phase. This list is not exhaustive.

Anticholinergics/antimuscarinics	Tricyclic/heterocyclic antidepressants	1st generation H1- antagonists†
Darifenacin	Alimemazine / Trimipramine	Tripelennamine
	-	-
Dicyclomine/Dicycloverine	Amitriptyline	Dimenhydrinate
Fesoterodine	Amoxapine	Clemastine
Flavoxate	Clomipramine	Bromazine
Isopropamide	Desipramine	Orphenadrine
Oxybutynin	Dosulepin/ Dothiepin	Doxylamine
Oxyphencyclimine	Doxepine	Carbinoxamine
Propantheline	Imipramine	Diphenhydramine
Propiverine	Lofepramine	Cyclizine
Tolterodine	Maprotiline	Chlorcyclizine
Trospium	Mianserin	Hydroxyzine
Solifenacin	Mirtazapine	Meclizine
	Nortriptyline	
	Protriptyline	
Alpha-blockers	CYP2D6 with narrow therapeutic index	Sensitive P-gp substrates
Tamsulosin	Thioridazine	Digoxin
Alfuzosin	Flecainide	Dabigatran
Doxazosin	Propafenone	
Terazosin	Imipramine	
Silodosin	Desipramine	
Strong CYP3A4 inhibitors	Other	
Itraconazole	Mirabegron (except for study dru	1g)
Ketoconazole	Botulinum toxin	
Ritonavir	Opioids	
Clarthromycin		

[figure not shown]
†Incidental use for motion sickness is accepted. P-gp: P-glycoprotein

## 9.3 AEs of Interest not covered by Standard MedDRA SMQs v23.0

The following is a list AE terms to programmatically flag subjects with AE's of interest (see Section 5.4.1).

Туре	Term	Code	AE of Interest	MedDRA 23.0 Search Criteria
LLT	Acute retention of urine	10001055	Acute urinary retention	Selected LLT (non-SMQ)
PT	Residual urine volume	10050832	Urinary retention	Selected PT's (non-SMQ)
PT	Residual urine volume increased	10067758	Urinary retention	Selected PT's (non-SMQ)
PT	Urinary retention	10046555	Urinary retention	Selected PT's (non-SMQ)

